3.1.1.1 Dose Escalation

This study will include an intra-patient dose escalation. The starting dose of baricitinib will be 2mg PO daily, a dose that has been well tolerated in previous studies of patients with autoimmune diseases. The first 7 subjects will be treated for a total of 12 weeks at this dose, unless they demonstrate cGVHD progression prior to this, at which time they will increase the dose to 4mg. If patients have a CR, they will continue at this dose until the primary efficacy endpoint. If patients have a PR or unchanged disease (see Section 6.3), the dose will increase to 4mg until the primary efficacy endpoint evaluation takes place at 24 weeks, unless they experience a DLT. If at least 1 patient of the first 7 in cohort 1 has a response, subjects will follow the original dose escalation schema. If 0 of these first 7 patients have a response, then patients will begin to be enrolled onto cohort 2, and will be started at the 4mg PO daily dose initially, unless they experience a DLT, at which time they will decrease the dose to 2mg.

As an early stopping rule for safety, if 2/3 or greater patients at any given dose level experiences a dose limiting toxicity requiring dose reduction or discontinuation, that dose will not be subsequently used.

Intra-patient Dose Escalation Schedule	
Dose Level	Dose of IND Agent
Level -1	1mg
Level 1	2mg
Level 2	4mg

3.2 DRUG ADMINISTRATION

Baricitinib will be given as 1 mg, 2mg or 4mg tablets to be taken orally once a day on days 1-28 of a 28 day cycle. Each daily dose should be taken at approximately the same time of day. There is no restriction in regards to taking the drug in relation to meals. Patients will be asked to complete a medication diary (see [Appendix J](#)).

Baricitinib tablets should be swallowed whole and not broken or chewed.

If a dose of baricitinib is missed, it should be taken as soon as possible on the same day, unless it is within 1 hour of the next dose, at which time the dose should not be made up.

Patients who take more than the prescribed dose of baricitinib should be instructed to seek medical care if needed and contact study staff immediately.

3.3 DOSE MODIFICATIONS

Patients who develop grade 2 toxicity (not including comorbidities that are present at baseline prior to treatment) for >7 days should hold baricitinib until the toxicity resolves (\leq grade 1) and then restart at the same dose level. Toxicities will be monitored at each study visit. If grade 2 toxicity recurs or worsens, the patient should be reduced to the next lower dose level, unless they are at dose level -1, at which time they should discontinue study drug. Should the toxicity recur

after dose reduction, the patient should be taken off treatment. In the case of multiple simultaneous grade 2 toxicities, these instructions will apply to each individual toxicity separately.

After the 4 week DLT assessment period for any dose level, patients who develop grade 3 non-hematologic or grade 4 hematologic toxicity (not including comorbidities that are present at baseline prior to treatment), or hemoglobin <6.5 g/dL, should hold baricitinib until the toxicity resolves (\leq grade 1 or baseline). If the toxicity resolves within 28 days, patients may restart at the next lower dose level, unless they are at dose level -1, at which time they should discontinue the study drug. Should the toxicity recur at grade 3 non-hematologic or grade 4 hematologic toxicity (not including comorbidities that are present at baseline prior to treatment), or hemoglobin <6.5 g/dL, after dose reduction, the patient should be taken off treatment.

Patients who develop grade 4 non-hematologic toxicity should discontinue and be taken off treatment.

Study drug may be held up to 28 days for resolution of grade 2 or grade 3 toxicity. Otherwise, if no resolution within 28 days, patients will be taken off treatment,

For infection related toxicities only: study drug should be held for any infectious toxicity of \geq grade 3. Infection will need to be controlled with appropriate management prior to restarting study drug for grade 3. If the infection occurs at the time of a study evaluation, all of the assessments at that time point will need to be postponed until the infection is controlled. Study drug can be restarted at the same dose level for grade 3 unless other criteria are met for dose reduction as above. Study drug may be held up to 28 days in the setting of uncontrolled infection; otherwise, if no resolution within 28 days, patients will be taken off treatment. Patients who develop grade 4 toxicity related to infection should discontinue and be taken off treatment.

Toxicities are defined as those events that are possible, probably, or definitely related to baricitinib.

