3 STUDY IMPLEMENTATION

3.1 STUDY DESIGN

This is a phase 1/2 single arm study to evaluate the safety and efficacy of baricitinib at doses of 2mg-4mg in patients with cGVHD after SCT. Doses of 0.5mg-20mg have been studied in patients with autoimmune diseases and have demonstrated a good safety profile (Baricitinib Investigator's Brochure, Eli Lilly and Company). Based on studies in patients with RA, there seems to be a plateau efficacy response at doses above 4mg daily, and it is the 4mg daily dose that was taken to the Phase 3 studies. In addition, in anecdotal experience with JAK inhibitors in patients with GVHD, low doses appear to be sufficient for response.

Patients will be enrolled in up to 2 sequential cohorts of up to 21 patients.

The first cohort of patients will be treated with baricitinib starting at a dose of 2mg daily for 12 weeks. For safety purposes, patients who experience a DLT within the first 4 weeks will be able to restart at 1mg daily, and will continue at this dose as tolerated (see Section 3.1.1). If they experience a DLT at this dose, they will be taken off treatment. Regarding efficacy, patients who have a complete response (CR) on 2mg daily at 12 weeks will continue the same dose until the 24 week time point for the primary efficacy endpoint. For patients who have a partial response (PR) or unchanged disease at 12 weeks, the dose will be increased to 4mg daily until the primary efficacy endpoint response assessment at 24 weeks. Following any dose increase to 4mg, patients who experience a DLT within the first 4 weeks will have a dose reduction back to 2mg daily. For patients who experience cGVHD progression at any time within the first 12 weeks on 2mg daily, the dose can be increased to 4mg daily up until the primary efficacy endpoint response assessment at 24 weeks, unless they experience a DLT. Prior to the 12 week response assessment, an initial response assessment will occur at 6 weeks, but there will be no dose changes unless there has been progression or toxicities, as outlined. If at least 1 patient in the first cohort has a PR or CR, the remainder of the study will follow the initial schema as above, and 21 evaluable patients will be treated as part of cohort 1. After the primary response assessment, patients who have unchanged or responding disease will have the option to continue baricitinib for an additional 6 months as tolerated.

[figure not shown]
[figure not shown]

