If no patients among the first 7 achieve a CR or PR on 2mg daily at the 12 week response assessment in the first cohort of patients, the second cohort will be enrolled starting at 4mg daily if no safety issues have arisen, with the same parameters for DLT monitoring. Similarly, if 0 of the first 7 treated in cohort 2 have a response, then no further patients will be treated in cohort 2.

If there is at least one patient with a response in the first 7 patients treated on cohort 2, then 21 evaluable patients will be treated in cohort 2.

Concurrent topical and ancillary treatments for cGVHD are allowed per standards of care and will be recorded (see Section 4). Other systemic immune suppression must stay stable or be tapered (systemic immunosuppression taper should be attempted no earlier than after 4 weeks on study), throughout the treatment with baricitinib (with up to 2 steroid pulses allowed for disease stabilization per Section 4.1).

Patients who discontinue therapy for any reason will be followed for up to 24 months after discontinuing baricitinib as indicated in section 3.5.

Peripheral blood samples will be collected prior to treatment, at 2 weeks, at 12 weeks and every 12 weeks thereafter to evaluate cytokine and cellular profiles, STAT phosphorylation, candidate chronic GVHD biomarkers. Pharmacokinetic studies will also be performed at each dose level on day 1 and after 15 days of treatment (Section 5.1.3).

*If ≥ 1 response in cohort 1, 2nd cohort will use identical schema as cohort 1

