3.1.1 Dose Limiting Toxicity

DLT will be defined as any grade ≥ 3 non-hematologic or grade ≥ 4 hematologic adverse event, or hemoglobin < 6.5 g/dL, within 4 weeks of starting any dose level (1mg, 2mg or 4mg) except those that are clearly and incontrovertibly due to extraneous causes. One inpatient dose de-escalation after a DLT will be permitted in patients who have not experienced cGVHD progression. In patients that have experienced disease progression, further dosing will cease in a patient at the occurrence of the first DLT.

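### For a related grade 4 non-hematologic event in the first 4 weeks at 4 mg, Sections 3.1 and 3.1.1.1 order a reduction to 2 mg while Section 3.3 takes the patient off treatment; after cGVHD progression, 3.1 also conflicts with 3.1.1

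*Combined protocol and SAP*

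**What the plan says.** All references are to the combined protocol and SAP.

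- **Section 3.1.1** counts every non-hematologic adverse event of grade 3 or above within 4 weeks of starting 1, 2 or 4 mg as a DLT, unless it clearly has another cause. It sets no upper grade limit. "One inpatient dose de-escalation after a DLT will be permitted in patients who have not experienced cGVHD progression" (read here as intra-patient). Once the disease has progressed, "further dosing will cease in a patient at the occurrence of the first DLT".
- **Section 3.1**, on patients raised to 4 mg: "Following any dose increase to 4mg, patients who experience a DLT within the first 4 weeks will have a dose reduction back to 2mg". On cohort 2: "the second cohort will be enrolled starting at 4mg daily if no safety issues have arisen, with the same parameters for DLT monitoring". On a DLT at the 2 mg starting dose: "patients who experience a DLT within the first 4 weeks will be able to restart at 1mg daily". A DLT at 1 mg ends treatment.
- **Section 3.1.1.1**, on cohort 2: patients are "started at the 4mg PO daily dose initially, unless they experience a DLT, at which time they will decrease the dose to 2mg".
- **Section 3.3**: "Patients who develop grade 4 non-hematologic toxicity should discontinue and be taken off treatment", and for infection "Patients who develop grade 4 toxicity related to infection should discontinue and be taken off treatment". Toxicity in that section means an event at least possibly related to baricitinib.
- **Section 3.9.1** lists unacceptable toxicity among the reasons for removal from therapy. It refers to both 3.1.1 and 3.3 without ranking them.

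**The concern.** A related grade 4 non-hematologic event soon after starting 4 mg meets two definitions at once: DLT under 3.1.1 and grade 4 toxicity under 3.3. One set of instructions lowers the dose and continues; the other stops the drug. Two investigators could each follow the protocol and do opposite things with the same patient.

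What is at stake is mainly safety. Following 3.1 or 3.1.1.1 as written gives more drug to someone whom 3.3 removes because of a drug-related grade 4 event. A secondary question is whether the choice changes who counts as evaluable for efficacy under 6.3.1.

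**Working it through.** **1. Do both rules reach the same patient?** Yes. A related event is not clearly due to another cause, so it is a DLT under 3.1.1. Being at least possibly related, it is also a toxicity under 3.3. Section 3.1 covers patients raised to 4 mg and 3.1.1.1 covers those who start there, so both routes to 4 mg are included.

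**2. Is the grade 4 sentence in 3.3 confined to the period after the DLT window?** Not by its wording. The paragraph before it is confined to that period, but names only grade 3 non-hematologic toxicity, grade 4 hematologic toxicity and hemoglobin below 6.5 g/dL. The grade 4 non-hematologic sentence is its own paragraph without a limit, and the infection sentence has none either.

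**3. Where do the instructions collide?**

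| Dose | No progression | After progression |
|---|---|---|
| 4 mg | 3.1 and 3.1.1.1 reduce; 3.3 stops for related grade 4 non-hematologic events: conflict | 3.1 reduces after any increase; 3.1.1 stops for any DLT: conflict |
| 2 mg | 3.1 only allows a restart at 1 mg, so stopping satisfies both sections | 3.1.1 stops; the 3.1 restart is optional |
| 1 mg | All stop | All stop |

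The two 4 mg conflicts differ in scope. Without progression, only related grade 4 non-hematologic events are affected. After progression, every DLT is affected, including grade 3 non-hematologic events.

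**4. Does evaluability change?** Section 6.3.1 requires 6 months of therapy and at least 75% of planned doses, with earlier progressors also included. It does not say whether planned doses are counted in dosing days or in mg. Over 24 weeks the plan is 24 × 7 = 168 dosing days. In mg/day × weeks, the plan is 12×2 + 12×4 = 72 for a cohort 1 patient raised at week 12, and 24×4 = 96 for cohort 2.

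*Stopped within the 4 mg window, without progression:*
- Cohort 1, 12 to 16 weeks dosed: 84/168 to 112/168 = 50% to 67% of days; 24/72 to 40/72 = 33% to 56% in mg.
- Cohort 2, at most 4 weeks: 28/168 = 17% of days; 16/96 = 17% in mg.
- All are below 75%, and none has completed 6 months.

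*Reduced to 2 mg and treated to week 24, no hold:*
- Days: 168/168 = 100%.
- Cohort 2 in mg, reduced at week 4: (4×4 + 20×2)/96 = 56/96 = 58%. Earlier reduction gives less, towards 48/96 = 50%.
- Cohort 1 in mg, reduced at week 12: (24 + 24)/72 = 67%. Reduced at week 16: (24 + 16 + 16)/72 = 56/72 = 78%.

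*With a 28-day hold:* (168 − 28)/168 = 83% of days. In mg, cohort 1 reduced at week 16 has (24 + 16 + 8)/72 = 67%. However, 3.3 provides that hold for grade 2 or 3 toxicity, so its use here would be an assumption.

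**5. Spare places (Section 10).** 31 − 21 = 10 if only cohort 1 is used; 31 − 28 = 3 if both cohorts are used.

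**The case against.** The strongest reply is that the documents already lean towards stopping. Section 3.9.1 is a list in which any one criterion removes a patient, and a patient taken off treatment by 3.3 meets it. Section 3.1.1 only permits de-escalation, so stopping complies with it. Section 3.3 allows holds for grade 2 or 3 toxicity and restarts after infection only for grade 3, so it offers no route back after a grade 4 non-hematologic event. Investigator discretion would also allow stopping.

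This stands as evidence of what was probably intended, and it supports the direction of the fix. It does not remove the conflict: 3.1 and 3.1.1.1 direct the reduction in mandatory terms, and no sentence says that 3.3 overrides them. Section 3.1 could equally be called the more specific rule, since it names the dose and the window.

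The situation is also narrow. The cohort 2 route opens only after 0 of 7 responses at 12 weeks. With independent patients that has probability 0.7^7 = 8% at a true 12-week response rate of 30% and 0.9^7 = 48% at 10%. That is fair, and it limits the weight of the point.

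A reader might infer that the choice decides whether the patient is evaluable for efficacy. The documents do not support this. It holds if dosing days are counted, but in mg most reduced patients also fall below 75%. A reader might also infer that de-escalation contradicts 3.3 at every dose. At 2 mg it does not, because the restart at 1 mg is optional.

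**Conclusion.** The conflict is real as written and should be fixed. At 4 mg without progression, a related grade 4 non-hematologic event, including infection, is sent to 2 mg by 3.1 and 3.1.1.1 and off treatment by 3.3. At 4 mg after progression, the sentence in 3.1 on dose increases conflicts with 3.1.1 for any DLT.

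The consequence is one of patient safety and consistent handling. A loss of evaluability from stopping instead of reducing is possible but conditional. Reduced patients can exceed 75% if days are counted; in mg with no hold they reach about 58% (cohort 2 reduced at week 4) to 78% (cohort 1 reduced at week 16). This assumes treatment to week 24 after the reduction.

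The documents give no basis for estimating how often the event occurs. The design's power, alpha and target of 21 evaluable patients do not change. The two-thirds safety rule counts DLTs that lead to either reduction or discontinuation, so it is the same under both instructions.

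**What to change.** In the DLT de-escalation text of 3.1 (including the sentence on increases to 4 mg), 3.1.1 and 3.1.1.1, add: *except related grade 4 non-hematologic toxicity (including infection), or any DLT after cGVHD progression, for which the patient is taken off treatment with no de-escalation (Sections 3.1.1 and 3.3)*. In 3.3, add *regardless of the DLT window* to the grade 4 non-hematologic sentence. The progression part is needed because a grade 4 exception alone would leave a grade 3 DLT after progression reduced under 3.1 and stopped under 3.1.1.

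This is the cautious direction and follows the two grade 4 stopping rules already in 3.3. The drafting cost is one clause in three sections and a phrase in a fourth. The clinical cost is that a patient who might have tolerated a lower dose stops. If that happens before 6 months without progression, the patient is not evaluable for efficacy and may use one of the 3 to 10 spare places under the accrual ceiling of 31.

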3.4 QUESTIONNAIRES

Patient self-report questionnaires administered in this study are part of the standard NIH chronic consensus recommended criteria for the evaluation of cGVHD in clinical trials. Questionnaires will be completed by patients with each cGVHD assessment and response evaluation (see section [3.7, Study Calendar](#)). These standardized assessments are designed to evaluate patient quality of life (FACT-BMT), functional performance (HAP) and symptoms (Lee cGVHD symptom scale). The purpose of these evaluations is to assess the potential benefit of the administered therapy as compared to the baseline. These forms have been extensively used, published and validated. These forms are also standard part of many NCI CCR cGVHD protocols ([Appendix I](#)). Patient questionnaires are only offered in English and are therefore not required in non-English speaking subjects that may unexpectedly be enrolled on the protocol.

3.5 FOLLOW-UP

All persons will be followed for adverse events for whichever is longer, 30 days after last dose of baricitinib or until return to baseline or stabilization of AE per section [6.1 0](#) by phone call.

Patients who discontinue therapy before completion of the 24 or 48 weeks will be asked to return for a follow up visit to complete their off treatment assessments within 30 days after the last dose

of study drug. Patients who discontinue therapy at the completion of 24 or 48 weeks will complete the off treatment assessments at the last scheduled visit. Following this, patients will be invited for a follow up visit at 3 months after last dose, then followed up by a phone call to the patient and/or the primary physician's office at 12, 18 and 24 months after completing baricitinib. If they choose not to follow up at 3 months, they will be followed up by phone call. The phone call will focus on a) survival status and cause of death if pertinent, b) ongoing systemic treatment for cGVHD and date of discontinuation, c) primary malignancy progression, d) any second primary malignancy, e) return to work part-time or full-time. Primary and contributing causes of death are to be recorded in the CRF and the patient's medical record.

3.6 TELEHEALTH

Telemedicine is the use of interactive audio, video, audio-visual, or other telecommunications or electronic technology by a licensed health care practitioner to deliver clinical services. This protocol will allow the team to practice telemedicine to communicate with patients in real time, to be able to monitor and collect data, as well as the ability to share the patients' health information with other health professionals. Providers may include primary providers, specialists/consultants and nurses. Other members of the healthcare team may also be present to aid with the communication devices, scheduling or records management. These visits may include the following: patient history, verbal exam, symptom reporting, education, and questionnaires.

The patient or patient's legal representative will be informed prior to the use of a telemedicine encounter and consent will be obtained as outlined in the Consent Process and Documentation (section 12.6).

Telemedicine visits will be arranged through our NIH Clinical Center Health Information Management Department and will be scheduled using NIH-approved remote platforms. Telemedicine visits may be used for follow-up visits if deemed appropriate by the PI. All telemedicine visits must be documented in CRIS like a normal onsite visit and the note should indicate that this visit was performed virtually. Remote visits will be conducted in compliance with NIH guidelines and FDA regulations.

Local Evaluations

A patient may be asked to come to the NIH CC for an in-person assessment or be referred to their local provider or outside lab, at the discretion of the investigator. All physical exams, assessments, and labs used for follow-up visits may also be performed with the patient's local physician or completed at outside labs. For laboratory evaluations conducted with local providers, interlaboratory variability is not a concern. In the case of any visits with participants' local providers or outside labs, records will be obtained.

3.7 STUDY CALENDAR

Assessments ¹	Screen (D -28 to -1)	BL BL / C1 D1	C1 D15	C2 D1	C2 D15	C3 D1	C3 D15	12 weeks C4 D1	C4D15	C5,6 D1	24 weeks C7 D1	C8,9 D1	36 weeks C10 D1	C11, 12 D1	48 weeks C12 D28	Off Treatment ¹³	Optional 3 month follow up ¹³
Visit Window			±5 days	±5 days	±5 days	±5 days	±5 days	±5 days	+/-5 days	± 7 days	± 7 days	± 7 days	± 7 days	± 7 days	± 7 days	± 7 days	± 7 days
Informed Consent	X	--	--	--	--	--	--	--	--	--	--	--	--	--	--	--	--
NIH Advanced Directives Form ¹⁷		X															
Baricitinib po qd ²	--	X	X	X	X	X	X	X		X	X ²	X ²	X ²	X ²	X ²	--	--
History and Physical Exam	X	X	X	X	X	X	X	X		X	X	X	X	X	X	X	X
Confirmation of cGVHD ³	X	--	--	--	--	--	--	--		--	--	--	--	--		--	--
Body Photography		X	--	--	--	--	--	--		--	X	--	--	--		X	--
Pulmonary Function Testing	X	--	--	--	--	--	--	X		--	X	--	X	--	X	X	--
Imaging ⁴	X																--
Pregnancy Test ⁵	X	X	X	X	X	X	X	X		X	X	X	X	X	X		--
cGVHD Therapies Recording	X		Throughout the study														
Vital Signs	X	X	X	X	X	X	X	X		X	X	X	X	--	X	X	X
Height	X	--	--	--	--	--	--	--		--	--	--	--	--		--	--
Weight	X	X	X	X	X	X	X	X		X	X	X	X	--	X	X	X
ECHO	X	--	--	--	--	--	--	--		--	--	--	--	--		--	--
ECG ⁶	X	--	--	X	--	X	--	X		--	X	--	--	--		--	--
cGVHD New Patient Data Form		X															
Karnofsky Performance Status	X	X	--	--	--	--	--	X		--	X	--	X	--	X	X	X
Additional screening studies ⁷	X		--	--	--	--	--	--		--	--	--	--	--		--	--
BK virus PCR (blood & urine)	X	X						X			X		X				

Assessments ¹	Screen (D -28 to -1)	BL BL / C1 D1	C1 D15	C2 D1	C2 D15	C3 D1	C3 D15	12 weeks C4 D1	C4D15	C5,6 D1	24 weeks C7 D1	C8,9 D1	36 weeks C10 D1	C11, 12 D1	48 weeks C12 D28	Off Treatment ¹³	Optional 3 month follow up ¹³
Visit Window			±5 days	±5 days	±5 days	±5 days	±5 days	±5 days	+/-5 days	± 7 days	± 7 days	± 7 days	± 7 days	± 7 days	± 7 days	± 7 days	± 7 days
CBC w/ differential, platelets	X	X	X	X	X	X	X	X	X	X	X	X	X	X	X	X	X
PT, PTT	X																
Serum Chemistry ⁸	X	X	X	X	X	X	X	X	X	X	X	X	X	X	X	X	X
CRP, C3, C4 ¹⁸	--	X	--	X	--	X	--	X		--	X	--	X	--	X	X	--
Urinalysis, fasting lipid panel	X	--X	--	--	--	--	--	X		--	X	--	X	--	X	X	--
TSH, free T4	X	--	--	--	--	--	--	--		--	--	--	--	--		--	--
cGVHD Assessment and Response Calculation ⁹		X	--	--	X	--	--	X		--	X	--	X	--	X	X	--
Lee scale, HAP, FACT-BMT		X			X			X			X		X		X	X	X
AE Monitoring	--		Throughout the study														
Concurrent Drugs	X		Throughout the study														
Dermatology, ophthalmology, dental, gynecology		X									X ¹⁴						X ¹⁴
Occupational therapy evaluation ¹⁵		X									X ¹⁴						X ¹⁴
Skin and Oral Biopsies, saliva collection and oral microbiome swabs ¹⁰	--	X	--	--	--	--	--	--		--	X	--	--	--	--	--	--
TBNK	--	X	X		--		--	X			X	--	X	--	X	X ¹⁶	X ¹⁶
Blood for Immunologic Studies (includes PD) ¹¹	--	X	X	--	--	--	--	X			X	--	X	--	X	X	
Blood for PK Studies ¹²	--	X C1D 1	X C1D 15	--	--		--	--X ¹² C4D1	X	--	--	--	--	--	--	--	--

Assessments ¹	Screen (D -28 to -1)	BL BL / C1 D1	C1 D15	C2 D1	C2 D15	C3 D1	C3 D15	12 weeks C4 D1	C4 D15	C5,6 D1	24 weeks C7 D1	C8,9 D1	36 weeks C10 D1	C11, 12 D1	48 weeks C12 D28	Off Treatment ¹³	Optional 3 month follow up ¹³
Visit Window			±5 days	±5 days	±5 days	±5 days	±5 days	±5 days	+/-5 days	± 7 days	± 7 days	± 7 days	± 7 days	± 7 days	± 7 days	± 7 days	± 7 days
Study drug dispensation/ return/accountability	--	X	--	X		X		X		X	X	X	X	X	X	X	--

- 1 Clinic visits can occur ± 5 days. All procedures at protocol-driven time points are performed at the NIH Clinical Center, but if circumstances make this impossible, these data points will be collected in collaboration with referring physicians.
- 2 Baricitinib at assigned doses for 6 months; another 6-month course of treatment will be allowed for patients with response. Only patients who continue therapy beyond 6 months will be required to have clinical monitoring tests during cycles 7 through 12.
- 3 Use NIH diagnostic criteria for cGVHD ([Appendix B](#) and [Appendix M](#): cGVHD New Patient Data Form). In addition, use [Appendix C](#) for clinical differentiation of acute versus cGVHD.
- 4 Chest CT done at screening; a chest CT may be done at response assessments if clinically indicated; a MRI may be done at baseline if clinically indicated
- 5 Pregnancy tests for females of childbearing potential. A female of childbearing potential (FCBP) is a sexually mature female who: 1) has not undergone a hysterectomy or bilateral oophorectomy; or 2) has not been naturally postmenopausal for at least 24 consecutive months (i.e., has had menses at any time in the preceding 24 consecutive months).
- 6 ECG at indicated intervals screening and as clinically indicated. Prolongation of QTc > 0.5 s or QTc interval increases from baseline > 0.06 s is considered as a safety concern.
- 7 Serologies for HIV, HBV, HCV, CMV PCR, blood and urine cultures, respiratory viral panel, CMV PCR. Cultures with no growth present at 48 hours will be deemed negative. BK virus PCR (urine) will be performed at baseline.
- 8 Including at **screening**: sodium, potassium, chloride, CO2, calcium, magnesium, phosphorus, blood urea nitrogen (BUN), creatinine, glucose, albumin, total protein, alkaline phosphatase, total bilirubin, AST (SGOT), ALT (SGPT), lactate dehydrogenase (LDH), and uric acid, creatine kinase (CK); at **baseline and on study assessments** (30-mL) include all screening studies as well as: drug levels if pertinent (tacrolimus, cyclosporine, sirolimus), immunoglobulin levels, CMV PCR at least every other week the first 12 weeks, then every 4 weeks until 24 weeks. CMV PCR will not be performed at remote visits unless clinically indicated. Note: Baseline studies performed within the appropriate timeframe at screening need not be repeated. (See section [2.4](#))
- 9 Includes primary and secondary measurement of response, performance scale, global rating ([Appendix D](#), [Appendix E](#), [Appendix F](#), [Appendix G](#), [Appendix I](#)). Note: The response assessment in [Appendix H](#) is not performed at baseline.
- 10 Skin and oral biopsies, saliva and microbiome swab collection will be performed at baseline and after 6 months of treatment, with intent to sample as close to the same area as possible. At baseline, the saliva and oral microbiome swabs will be collected at the time of the oral biopsy, if performed.

- 11 Blood (48 mL in 6 CPT tubes) for immunologic studies will be drawn prior to first drug at all timepoints. PD baseline assay will be performed using some of the blood for immunologic studies. PD studies at the peak blood level of baricitinib will be performed on a 6ml (green topped heparin) tube collected at 2 hours post drug at Cycle 1 Day 1. PD studies will be repeated at any increase in drug dose.
- 12 For determining serum baricitinib levels (PK), on the first day of each dose level a 3-mL blood (EDTA) sample will be taken pre-dose, then at 1, 2, and 4 hours after the dose. A sample will be collected at 24 hours after the first dose in up to 10 patients as feasible, but is not required on protocol. A trough level blood sample will be collected at the next scheduled visit at 15 (+/-1) days of continuous treatment at the initial dose. The sample will always be collected immediately before the next baricitinib dose to measure a 24 hour PK time point. This collection will also occur following 15 (+/-1) days of continuous treatment after an increase in dose level. The PK sample at week 12 is not collected if no change in dose level occurred. In the event of a serious adverse event or at the end of study, an additional sample may be collected within 24 hours of the last dose at the discretion of the investigator (See Section 5.1). Every effort will be made to collect samples as prescribed in the timeline. Samples that are collected \pm 15 minutes of collection time will not be considered a protocol deviation.
- 13 Patients who discontinue study drug before completion will be asked to return to complete off treatment assessments within 30 days after the last dose of study drug. Patients who complete therapy (24 or 48 weeks) will complete the off treatment assessments at the last scheduled visit. All patients, regardless of reason for study drug discontinuation will be followed for adverse events by phone call for at least 30 days for adverse events and invited for an optional follow up visit a 3 months after study drug discontinuation followed by phone calls to the patient or patient's primary physician at 12, 18 and 24 months (if patients choose not to follow up at 3 months, they will be followed up by phone call) (see Section 3.5)
- 14 Subspecialty evaluations are required at baseline. Subsequent evaluations at 6 months and off treatment will be arranged based on organ involvement and medical need of individual patients. All response assessments will be performed by the transplant clinical team.
- 15 Functional assessment (ACS and HAQ), fatigue assessment (MDFI), and upper extremity use (DASH/MAM) (See Appendix L)
- 16 If PI deems TBNK is necessary at this visit.
- 17 As indicated in section 12.3, all subjects will be offered the opportunity to complete an NIH advanced directives form. This should be done preferably at baseline but can be done at any time during the study as long as the capacity to do so is retained. The completion of the form is strongly recommended, but is not required.
- 18 CRP, C3, C4 will not be performed at remote visits unless clinically indicated.

